The goal of this study is to compare two comprehensive strategies to promote CM implementation as an adjunct to pharmacotherapy within OUD centers. Using a cluster randomized design, 30 OUD treatment centers across New England will be randomized to one of the two implementation conditions: 1) ATTC control condition: SAMHSA-funded Addiction Technology Transfer Centers (i.e., didactic workshop + performance feedback + staff coaching); 2) E-ATTC experimental condition: ATTC strategy enhanced by external leadership coaching (ELC; i.e., leadership coaching focused on sustainment planning) and pay-for-performance (P4P; i.e., monetary bonuses for achieving pre-defined implementation goals). Specific research aims of the study are:

1. Primary Aim: To test effectiveness of E-ATTC, relative to the ATTC condition, on implementation outcomes.

- a. Primary Hypothesis: Relative to ATTC, E-ATTC will achieve superior: CM Exposure (i.e., patient-level measure of number of CM sessions received during 9-month Implementation phase) CM Competence (i.e., staff-level measure of CM quality during 9-month Implementation phase), and CM Sustainment (i.e., patient-level measure of number of CM sessions received during 12-month Sustainment phase).

2. **Secondary Aim:** To test effectiveness of E-ATTC condition, relative to ATTC, on patient outcomes.
 - a. Secondary Hypothesis: Relative to ATTC, E-ATTC will achieve superior: Opioid Abstinence (i.e., days of abstinence) and Opioid-Related Problems (i.e., count of problems) at 3 and 6-month follow-up.
3. **Exploratory Aim:** To test the extent to which theorized mechanisms of change (i.e., implementation climate, leadership engagement) mediate the implementation condition (i.e., ATTC vs. E-ATTC) to outcome (i.e., implementation outcome, patient outcome) relationship.
 - a. Exploratory Hypothesis: Implementation climate and leadership engagement will partially mediate the relationship between implementation condition and each outcome in the Primary and Secondary Aims.

B) Detailed Study Methodology

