1. **Study Purpose.** The primary purpose of this study is to experimentally evaluate two different comprehensive training models to train opioid treatment centers in an evidence-based behavioral treatment called contingency management (CM), which is the provision of motivational incentives for reaching specific treatment benchmarks. An exploratory goal of this study is to test whether theorized mechanisms of change – implementation climate and leadership engagement – mediate the effect of implementation condition on outcomes. Conduct of this study will address critical public health needs by (a) informing how CM, an evidence-based practice, should be implemented in OUD treatment centers, (b) improving the outcomes of OUD patients receiving treatment in the community, and (c) advancing knowledge about why and how implementation strategies work.
2. **Overview of Study Design.** A Type 3 Hybrid Trial will be conducted collecting data on both implementation and patient outcomes. We will use a 3-cohort staggered cluster RCT design. The unit of randomization will be opioid treatment centers. Centers will receive one of two comprehensive training conditions: the standard training provided by the New England Addiction Technology Transfer Center (ATTC training) or an enhanced condition that also provides leadership coaching and provider incentives (E-ATTC training). The primary research activities will be measuring the effectiveness of the training initiatives by gathering data from organizations, providers and patients.

Every 12-16 months, 10 OUD centers will be randomly selected to initiate study activities (10 centers X 3 cohorts = 30 centers). Prior to randomization, each center will complete a Baseline Organizational Assessment (described further in the Measures section) to collect organizational background data (e.g., years in operation, number of patients served annually, number of staff, medications prescribed, implementation readiness). Using these data, urn randomization procedures (balancing on number of patients served and percent of patients receiving methadone) will be used to randomize centers to either the ATTC or the E-ATTC condition. Centers in both conditions will complete a 5-month Preparation phase, a 9-month Implementation phase, and a 12-month Sustainment phase (26 months total). In both conditions, providers will record their delivery of CM in the electronic medical record and will audio record one CM session per month.

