Incentive amounts are designed to enable staff to, on average, earn bonuses that during a 12-month period would comprise about 6% of their mean annual base salary of US \$45,000. Prior P4P research^{18,19} has suggested that bonuses between 4 and 7% are large enough to significantly improve staff performance, yet modest enough to be practical for community treatment centers to implement. Provision of incentives will follow the exact same schedule of provision of performance feedback reports described in 7a. Sessions must be submitted by the last day of the month and must be from that calendar month. Within 2-4 weeks following submission of recordings, providers in the E-ATTC condition will receive email notifications from research staff containing their performance feedback reports, as well as confirmation of their achievement of CM Exposure and CM Competence for the prior month. CM staff enrolled in the E-ATTC condition will receive payments via cash, check, or Clincard.

8. Data Collection Procedures.

- a. *Organizational background form.* Prior to randomization, leaders at each center will collaboratively complete an Organizational Background Form via Qualtrics. Data collected will include, but not be limited to: number of patients, proportion of patients on different OUD medications, number of staff, average staff tenure, and years in operation.
- b. *Staff surveys.* After randomization, CM staff and leadership staff will complete two online Qualtrics surveys: one at the start of the Preparation phase and one at the midpoint of the Implementation phase. The first survey (30-45 minutes) will contain the following measures: Provider Demographics, Organizational Readiness for Change, Attitudes towards CM, and putative mediators (i.e., Implementation Climate, Leadership Engagement). The second survey (15-30 minutes) will only evaluate the putative mediators. Participating staff will receive \$25 for the first and \$20 for the second survey. We attained 82% or higher completion rates on comparable staff follow-up surveys in the New England ATTC pilot.

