- b. For the **Primary and Secondary Aims**, we test a series of multilevel models in which patients (Level 1) are embed within staff (Level 2) and within centers (Level 3). Consistent with Raudenbush and Bryk's multilevel modeling approach,³² the proportion of variance to-be-explained at each level will be examined as an initial step. Next, following a decomposed-first strategy that advocates for starting with moderation-focused hypotheses to avoid biases associated with conflated effects,³³ we conduct multilevel regressions testing the extent to which our covariates significantly moderate the hypothesized relationship between condition and outcome. We test covariates at three levels: organizational (e.g., years of operation, number of patients, medications prescribed, implementation readiness), staff (e.g., tenure, education, CM attitudes), and patient (e.g., age, race, biological sex, problem severity). If moderation is not found, covariates will be controlled for as predictors. Condition assignment (ATTC vs. E-ATTC) will be the primary independent measure of interest for analyses. In addition to reporting statistical significance, we will report the effect size (ES) using Cohen's d .³⁴
- c. For the **Exploratory Aim**, we again test a series of 3-level models. For each mediator, the average correlation within group (r_{wg}) will be computed to determine whether aggregation of staff level responses to the organizational-level is warranted. Values of r_{wg} range from -1.00 to 1.00, with values $\geq .60$ representing acceptable agreement.³⁵ Centers with r_{wg} values $< .60$ will be excluded from analysis. Exploratory analyses will apply a Baron and Kenny³⁶ style mediation approach,

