which uses centering within context and includes a group mean at level-3 (CWC[M]).³⁷ Procedurally, first the outcome will be regressed on the condition variable (ATTC vs. E-ATTC) in a multi-level regression. Next, the outcome will be predicted by both condition and the group mean centered mediator (e.g., implementation climate) in a multi-level regression. Third, the mediational effect will be calculated by subtracting the estimated coefficient associated with condition in step two from the estimated coefficient associated with condition in step one. This method will allow the between-group mediation effect to be partitioned from the within-group mediation effect, which is important since between-group mediation is the effect of interest. Although significance of the mediation effect will be calculated using the Freedman and Schatzkin³⁸ *t* statistic, we also will report ES, which are not influenced by power.

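### The mediation analysis enters climate or leadership engagement one at a time, so it cannot tell two mechanisms from one mechanism seen through two correlated scales

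*Combined protocol and SAP*

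**What the plan says.** The Exploratory Hypothesis in the Specific Aims names two mediators for every outcome: "Implementation climate and leadership engagement will partially mediate the relationship between implementation condition and each outcome in the Primary and Secondary Aims". Under section 9.c (Putative mediators), CM staff and leaders rate both scales, at the start of Preparation and at the midpoint of Implementation. Section 8.b (Staff surveys) puts both scales in the same online surveys and says of the midpoint one: "The second survey (15-30 minutes) will only evaluate the putative mediators".

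The analysis is in section 10.c. The agreement check is made scale by scale ("For each mediator, the average correlation within group"). Step one regresses the outcome on condition. In step two, "the outcome will be predicted by both condition and the group mean centered mediator (e.g., implementation climate) in a multi-level regression". Then "the mediational effect will be calculated by subtracting the estimated coefficient associated with condition in step two from the estimated coefficient associated with condition", where the last-named coefficient is the one from the first regression. On inference, "significance of the mediation effect will be calculated using the Freedman and Schatzkin" t statistic, and the plan explains that "between-group mediation is the effect of interest".

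The mediator in step two is singular, with climate given as an example. Section 10.c contains no model with both mediators, no report of their correlation, and no caution about reading two overlapping results.

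**The concern.** The two scales are close in content: one asks whether CM is backed and rewarded in the center, the other whether leaders stand behind it. The raters and the occasions are the same, so a positive correlation between center means is plausible. E-ATTC adds leadership coaching and provider bonuses, and the hypothesis expects it to act through both.

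If both scales move with condition and are correlated, the slope of whichever one is in the model also carries part of the effect of the one left out. The drop in the condition coefficient is then credited to each mediator in turn. Study Purpose lists "advancing knowledge about why and how implementation strategies work" among the trial's contributions. At stake is a report of two mechanisms when the data may support only one.

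**Working it through.** The documents give no power calculation, significance level or effect size for the mediation aim, so there is no figure of the plan's to reproduce.

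**Inputs from the documents:** 30 centers; two mediators; one mediator per step-two model; difference-in-coefficients estimator; Freedman-Schatzkin t.

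**Assumptions:** 15 centers per arm; two-sided 0.05; analysis simplified to center level with unit within-arm SDs; the path sizes; the within-arm center-level correlation ρ between the scales, which the documents do not give.

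**Parallel mediators.** Let T be condition, climate M1 = a1·T + e1, leadership M2 = a2·T + e2, with corr(e1, e2) = ρ, and Y = c′·T + b1·M1 + b2·M2 + error.

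- Step one, coefficient of T: c′ + a1·b1 + a2·b2.
- Step two with M2 alone: the slope of M2 is b2 + ρ·b1, and the coefficient of T is c′ + a1·b1 − ρ·a2·b1.
- Difference credited to M2: a2·(b2 + ρ·b1).

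If leadership has no effect of its own (b2 = 0), it is credited with ρ·a2·b1. Climate's true mediated effect is a1·b1, so with a1 = a2 the share is ρ. With a1 = a2 = 1 and b1 = 0.8, climate's true effect is 0.80 and leadership's is 0:

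| ρ | Credit to leadership, ρ × 1 × 0.8 | Simulated mean | Declared a mediator, Freedman-Schatzkin | Declared a mediator, both paths significant |
|---|---|---|---|---|
| 0.5 | 0.40 | 0.41 | 38% | 30% |
| 0.7 | 0.56 | 0.57 | 66% | 51% |
| 0.8 | 0.64 | 0.64 | 79% | 61% |

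With both mediators in the model, the rule in the last column flags leadership in about 3% to 5% of runs.

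**Other assumed values**, Freedman-Schatzkin test of the inert mediator at ρ = 0, 0.3, 0.5, 0.7, 0.9 (4,000 runs each):

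- a1 = a2 = 1, b1 = 0.6: 5%, 12%, 25%, 48%, 71%.
- a1 = a2 = 0.5, b1 = 0.6: 4%, 9%, 18%, 38%, 55%.
- a1 = 1, a2 = 0, b1 = 0.6: 2%, 6%, 12%, 22%, 35%. Here the mean credit is 0 at every ρ, but the test still rejects too often once ρ is 0.5 or more.

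**Chain instead of parallel.** Suppose leadership drives climate with slope d, condition raises leadership by a = 1, and only climate acts directly on the outcome (b1 = 0.8). Leadership's true mediated effect is a·d·b1 = 0.40, 0.56, 0.64 at d = 0.5, 0.7, 0.8. The single-mediator model returns 0.40, 0.56, 0.64, which is right. The joint model's leadership-specific effect is about 0.00, significant in about 4% of runs, which would wrongly clear leadership.

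So a single-mediator result of 0.40 to 0.64 is the expected finding under both structures. The total joint mediated effect (step-one coefficient minus the condition coefficient with both mediators in) is unbiased under either; its simulated SD was about 0.36 to 0.40.

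**Precision lost on mediator-specific effects in the joint model.** The slope's standard error grows by 1/√(1 − ρ²): 1/√0.75 = 1.15, 1/√0.51 = 1.40 and 1/√0.36 = 1.67 at ρ = 0.5, 0.7, 0.8. With a1 = a2 = 1 and b1 = 0.6, the joint model detects the true mediator in 61%, 54%, 42% and 19% of runs at ρ = 0, 0.5, 0.7, 0.9.

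**The case against.** The strongest objection is causal. Calling leadership a false mediator presumes that the two mediators act side by side. External leadership coaching is directed at leaders, and engaged leaders could well produce a climate in which CM is supported. Nothing in the documents excludes that chain, and because both scales are taken on the same occasions the data cannot order them. Under the chain the single-mediator model is right and the joint model's specific effect misleads. This stands, and it rules out simply replacing the one model with the other.

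A reader might infer that each mediator is credited with the whole of the other's effect, or that the plan overstates mediation by adding the two. Neither follows. The credit is a share, about ρ when condition moves both equally, and zero on average when condition does not move the inert one. The plan never sums the two effects.

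Three lesser points also stand. One-at-a-time fitting is inferred from the singular wording and the absence of a joint model; no sentence says it outright. A mediator with exactly no effect is a limiting case, since the hypothesis expects both to contribute. And the joint model is not a clean separator: each center mean rests on 2 to 5 providers and 2 leaders. With an assumed reliability of 0.6 to 0.8 and ρ of 0.7 to 0.8, it still credited the inert mediator with 0.13 to 0.20 on average and flagged it in about 6% to 9% of runs. The bias from single models remains larger.

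**Conclusion.** The concern holds in a limited form. As written, section 10.c can show that each scale, taken alone, accounts for some of the condition effect. It cannot show whether that reflects two mechanisms, one mechanism and a correlated bystander, or one mediator working through the other.

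Under parallel action, with both scales raised 1 SD, a climate slope of 0.8 and correlations of 0.5 to 0.8, an inert mediator receives 50% to 80% of the other's effect and passes the plan's test in about 38% to 79% of trials (30% to 61% if both paths must be significant). These rates rest on assumed correlations and effects. At zero correlation the problem disappears.

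The documents do not support the stronger conclusion that the single-mediator results are wrong and should be dropped, because under a leadership-to-climate chain they are correct. The aim is exploratory, and the primary and secondary comparisons do not depend on it. This is a worthwhile, low-cost addition.

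**What to change.** In section 10.c, for each outcome:

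- Add one step-two model with condition and the center means of both mediators.
- Report the total joint mediated effect as the main mediation estimate.
- Report the between-center correlation of the two scales.
- Show the mediator-specific effects from the single and joint models side by side. State that the single-mediator effects overlap, and that the joint-model effects assume neither mediator causes the other.
- Do not claim two distinct mechanisms from separate models alone. If a joint model was always intended, say so in the text.

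The cost is one extra model per outcome on data already collected. The joint mediator-specific estimates will be imprecise with at most 30 centers. There will be fewer if a center must pass the 0.60 agreement rule on both scales, so the plan should say how that rule applies to the joint model. These estimates also keep some bias when center means are measured with error.

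### The mediation test in the Exploratory Aim never checks whether condition changes the mediator, so it can run well above 5% false positives when the mediator is at least moderately related to outcome

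*Combined protocol and SAP*

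**What the plan says.** The procedure is in Section 10.c (Analytic Plan, Exploratory Aim) of the combined protocol and SAP. It has three steps.

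1. "first the outcome will be regressed on the condition variable (ATTC vs. E-ATTC) in a multi-level regression".
2. Next, "the outcome will be predicted by both condition and the group mean centered mediator".
3. The mediated effect is obtained by "subtracting the estimated coefficient associated with condition in step two from the estimated coefficient associated with condition in step one".

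The difference is then tested: "significance of the mediation effect will be calculated using the Freedman and Schatzkin" t statistic, with effect sizes reported as well. The section calls this a Baron and Kenny style approach. It says a center mean of the mediator enters at level 3, and gives as the reason that "between-group mediation is the effect of interest".

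The section does not give the formula of the statistic, an alpha level, sidedness or degrees of freedom. It does not require step 1 or the mediator coefficient to be significant first. It does say that centers with within-group agreement (r_wg) below .60 are excluded from this analysis.

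**The concern.** Mediation needs two links: condition changes the mediator, and the mediator relates to outcome given condition. The listed steps estimate only the second link directly. The first enters unseen, through the change in the condition coefficient.

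The mediator is aggregated to the center and condition is assigned to centers ("30 OUD treatment centers across New England will be randomized to one of the two implementation conditions"), so the first link is a comparison of about 15 center means with 15 others. Chance differences of that kind are large. A test that treats the observed mediator values as fixed does not count them as error. If climate or leadership engagement predicts outcome, a chance difference between arms can be declared a mechanism.

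The Exploratory Hypothesis in Section 2.A names two mediators for each of the three primary and two secondary outcomes, so at least 2 × 5 = 10 such tests are in view. Section 2.B lists learning why and how implementation strategies work among the purposes of the study. The risk is a report that climate or leadership carried the effect of E-ATTC when E-ATTC did not move them.

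**Working it through.** The plan states no error rate for this test, so there is no figure of its own to reproduce.

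**Inputs from the document.** 30 centers (Section 2.A); the three steps and the named test (Section 10.c); possible loss of centers through the r_wg rule (Section 10.c); and one mediator association, β = .18 between leadership engagement and staff-level fidelity, from another project (Section 9.c).

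**Assumptions.** Two-sided 5%; t with K − 2 degrees of freedom; equal allocation (the document specifies urn randomization but no ratio); 20 or 24 centers as examples of what remains after exclusions; step 2 contains the center mean of the mediator; and the usual form of the statistic,

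t = (τ − τ′) / √(se_τ² + se_τ′² − 2·se_τ·se_τ′·√(1 − r²)),

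where τ and τ′ are the condition coefficients from steps 1 and 2, and r is the correlation of condition with mediator.

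**Why it fails: one case by hand.** Take 15 centers per arm, unit residual SDs, slope b = 0.6 and no true effect of condition on the mediator.

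- The standard error of the mediator difference between arms is √(1/15 + 1/15) = 0.365 SD. Suppose the observed difference is exactly that, so its own t is 1.0.
- τ − τ′ = 0.365 × 0.6 = 0.219.
- se_τ = √(1 + 0.36) × 0.365 = 0.426. With r = 0.180, √(1 − r²) = 0.984 and se_τ′ = 0.365/0.984 = 0.371.
- The denominator is √(0.1813 + 0.1378 − 0.3110) = 0.090, so t = 0.219/0.090 = 2.43, beyond the 28-df critical value of 2.05.
- A standard error that carries both paths is about √(0.36 × 0.1333 + 0.1333 × 0.0333) = 0.229, which gives 0.219/0.229 = 0.96.

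So an unremarkable one-standard-error imbalance is declared significant mediation.

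**Simulation at center level.** M = a·X + e and Y = 0.5·X + b·M + u, with a = 0, unit-variance errors and 40,000 replicates per cell. Joint significance requires condition-to-mediator and mediator-to-outcome (given condition) each at two-sided 5%.

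| Slope b (SD) | Planned test, 30 centers | 24 centers | 20 centers | Joint significance, 30 centers |
|---|---|---|---|---|
| 0 | 2% | 2% | 2% | 0.2% |
| 0.18 | 6.6% | below 5% | about 3.5% | about 0.7% |
| 0.3 | 14% | 10% | 7% | 1.5% |
| 0.4 | 24% | 16% | 11–12% | 2.4% |
| 0.6 | 38% | 29% | 22% | 3.8% |
| 0.8 | 41% | 36% | 29% | 4.7% |

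A slope b corresponds to a correlation of b/√(1 + b²), so 0.8 is about .63. With 30 and 24 centers the rate peaks near slope 0.8 to 0.9. With 20 it rises a little further, to about 31% near slope 1.0. It then falls; at a correlation of .9 with 30 centers it is 21%.

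**Patient-level check.** Mixed models with 30 centers of 25 patients, at mediator correlations of .3, .5 and .7 with the true center effect, gave 11%, 25% and 37% at ICC .05, and 13%, 27% and 39% at ICC .20. There were 150 replicates per cell, with a Monte Carlo standard error of 2.5–4 points and some convergence warnings. The inflation is not an artifact of analyzing center means.

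**Role of the missing step.** With 30 centers, about nine in ten of the false mediation findings had a non-significant condition-to-mediator path.

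**The case against.** The strongest counter-argument is about size. The document gives a single association, .18, and there the planned test rejects 6.6% of the time with 30 centers and less than 5% with 20–24. The rates above 20% need associations about twice that or more, which the document does not supply. It gives none for implementation climate, and none for either mediator with the patient outcomes. This stands as a limit on what can be claimed. It does not clear the test: .18 is a staff-level figure, its center-level counterpart is unknown and could be larger, and the investigators' own theory is that these mediators drive outcome.

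A reader might infer that the test is badly inflated whenever condition leaves the mediator unchanged. The document does not support that. The excess also requires a mediator that predicts outcome at least moderately; with no such relation the rate is below nominal.

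A second counter-argument is that a Baron and Kenny style analysis implies preliminary conditions. The section lists its steps and includes none. Requiring a significant step 1 would hold the rate to at most 4.7% when condition has no direct effect. With a direct effect of about 1 SD, it would still be 26–29% at correlations of .5 to .7.

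Third, effect sizes are to be reported alongside the t statistic. That is useful but corrects nothing, because the same chance imbalance enters τ − τ′.

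Finally, the analysis is exploratory. That limits the consequences, but does not make the test valid.

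**Conclusion.** The concern holds in a conditional form. Section 10.c never tests whether condition changes the mediator, and the named statistic omits the sampling error of that path. When condition does not move the mediator but the mediator predicts outcome with a center-level slope of about 0.3 SD or more, the planned test finds mediation about 14–41% of the time with 30 centers. Over slopes of 0.3 to 0.8 the corresponding figures are about 10–36% with 24 centers and 7–29% with 20. Losing centers to the r_wg rule lowers the rate without curing it.

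These figures rest on the assumed 5% level, degrees of freedom, equal allocation and form of the statistic. The true center-level association is unknown, so they describe what can happen and are not a forecast for this trial. The consequence is a possible false statement about mechanism. The primary and secondary comparisons of E-ATTC with ATTC do not depend on this test.

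**What to change.** In Section 10.c:

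- Add a step that regresses the center-mean mediator on condition.
- State that step 2 uses the center mean of the mediator to estimate the between-center path. With only the within-center-centered mediator in the model, τ − τ′ would be exactly zero in balanced data.
- Decide on between-center mediation by joint significance of the two paths, or by a Monte Carlo confidence interval for their product a × b, using center-level degrees of freedom. Drop the Freedman-Schatzkin t as the test.
- State the alpha level and sidedness.

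No new data are needed; the cost is wording and minor programming.

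There is also a loss of nominal power when mediation is real, and the sponsor should know this. With 30 centers, a = 0.8 and b = 0.4, the chance of a significant result falls from about 47% to about 28%; at a = 1.0 and b = 0.6 it falls from 82% to 62%. So the results given up are not all false positives. But the higher figures come from a test that does not hold its 5% level, so they are not power that the plan can properly claim.
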